### Cycle 4 Procedures

- Review concomitant medications
- AE Recording
- A 12-lead ECG will be recorded prior to AGI-134 administration (up to 1 hour before dose) and 2 hours post dose (± 30 minutes)
- Symptom-directed physical examination pre-dose only
- Examination of injection site will be performed 1 hour pre-AGI-134 administration and 1 hour (±30 min) post AGI-134 administration
- Vital signs (blood pressures, pulse rate, O2 saturation, oral temperature in °C, respiratory rate) will be assessed pre-dose and 2 hours post dose.
- ECOG performance status

agalin A subsidiary of Bio	nnune DLINERX	PRIVILEGED & CONFIDENTIAL
Investigational Product: AGI-134		Protocol No. AGI-134.FIM.101
Phase: I/IIa	doses of AGI-134 in unresectable/metastatic solid tumours.	Version 6.1 31 May 2021

- Photography of superficial injected and non-injected lesions (if a different lesion is injected, the previous injected lesion should be photographed as well): 1 hour (±30 min) pre-AGI-134 administration and 1 hour (±30 min) post AGI-134 administration
- Review general instructions before study drug administration (see section 5.7)
- AGI-134 administration (every effort should be made to inject the same lesion as in previous cycle).
- Urinalysis
- Pregnancy test in urine
- Blood will be drawn for:
  - Disease markers according to each subject's disease
  - o PT/INR and aPTT (results should be available before injection)
  - o CBC with differential
  - Biochemistry panel
  - o T3, free T4 and TSH
  - o C5a pre dose and 2 hours post dose
  - PK of AGI-134 and metabolites: up to 1 hour prior to AGI-134 administration and 2 hours post dose

## Week 18, 27, 36 and 45 Visits

Visits will be performed at the following weeks: 18, 27, 36 and 45 (i.e. every 9 weeks beginning from Cycle 4).

## Week 18, 27, 36 and 45 Visits Procedures:

- Review of change in concomitant medication
- AE Recordings (AEs up to 30 days post last dose of study drug and SAEs up to 90 days post last dose of study drug)
- Examination of injection site
- ECOG performance status
- Photography pictures of all injected superficial tumour, if applicable.
- Tumour Imaging assessment
- RECISTv.1.1 assessment will be done using imaging and/or superficial lesion measurement according to the tumour type.

agalin A subsidiary of BIO		PRIVILEGED & CONFIDENTIAL
Investigational Product: AGI-134	A Phase I/IIa, multicentre, two-parts, open label study designed to evaluate the safety and tolerability of escalating	Protocol No. AGI-134.FIM.101
Phase: I/IIa	doses of AGI-134 in unresectable/metastatic solid tumours.	Version 6.1 31 May 2021

## 5.4 Termination or Early Termination Study Visit (Week 54 or ET)

The total study participation period is 54 weeks. Treatment with AGI-134 will be provided for up to 4 cycles (12 weeks). A Termination visit will be performed at Week 54 for all subjects.

In case of Early Termination (ET), all reasons for treatment discontinuation will be documented in the source documents yet only one reason (the most severe) for ET should be recorded in the eCRF. If one of the reasons for early termination is an AE, this should be chosen as the reason. Every effort should be made to follow-up these subjects until resolution or stabilisation of the AE.

At this visit, the following activities will be performed. Exceptions for assessments may be provided in case these assessments were done 1-2 cycles prior to Termination visit and after discussion and approval by the study MM.

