## 5.3 Core Study

The duration of the Core Study will be up to 54 weeks.

AGI-134 administration is divided into cycles (each cycle is 3 weeks long). Each cycle may be extended if additional safety assessment is needed.

AGI-134 is administered for up to 4 cycles. For administration and tissue biopsies information and guidance, please refer to the instructions in the *Administration of AGI-134 and Tumour Biopsy Procedures in Study AGI-134.FIM.101* document.

Visits will be named as follows:

- AGI-134 Administration Visits: Visit Cycle 1-Day 1, Visit Cycle 2-Day 1, Visit Cycle 3-Day 1, Visit Cycle 4-Day1
- Other Visits:
   Visit Cycle 1-Day 3, Visit Cycle 1-Day 8, Visit Cycle 1-Day 15, Visit Week 18,
   Visit Week 27, Visit Week 36, Visit Week 45, Week 54 (Termination)

## 5.3.1 Cycle 1

This visit will begin after completion of the Baseline visit. Treatment initiation may be done on the same day of Baseline visit, but Baseline procedures should be completed prior to investigational product administration. On this day, AGI-134 will be administered. The following activities will be performed during this visit. Details on the specific days for each assessment are presented in the SoA (APPENDIX A).

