- Tumour tissue biopsy will be performed 48 ±24 hrs post AGI-134 administration, from injected lesions only. This biopsy is mandatory for superficial injected lesion and is also requested for deep lesions, unless it is not considered in the best interest for the patient by the PI.

## 5.3.3 Cycle 1 - Day 8 and Day 15

The following procedures will be performed:

- Review of change in concomitant medication
- AE Recordings
- Symptom-directed physical examination
- Examination of injection site
- Photography of superficial injected and non-injected lesions if applicable
- Vital signs (blood pressures, pulse rate, O2 saturation, oral temperature in °C, respiratory rate)
- Blood will be drawn for:
  - CBC with differential
  - Biochemistry panel
  - o Anti-Gal antibodies IgG/IgM (Cycle 1 Day 8 only)

## 5.3.4 Cycles 2, 3 and 4

AGI-134 will be administered on Day 1 of each cycle. The following procedures will be performed during these visits; each assessment should be performed before administration of the investigational product unless otherwise specified. Detailed activities are presented in the SoA (APPENDIX A).

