# 12 APPENDICES

APPENDIX A: Schedule of Assessments

agalin A subsidiary of BIG		PRIVILEGED & CONFIDENTIAL
Investigational Product: AGI-134	A Phase I/IIa, multicentre, two-parts, open label study designed to evaluate the safety and tolerability of escalating doses of AGI-134 in unresectable/metastatic solid tumours.	Protocol No. AGI-134.FIM.101
Phase: I/IIa		Version 6.1 31 May 2021

Table 6: Schedule of Assessment - Part 1: Accelerated Dose Escalation of AGI-134

Study Period:	Screening Phase	Baseline Assessments					3-	We	ek (	Cyc	les				9-Week F.U Cycles	Termination Visit	Long-Term Follow-up
Treatment Cycle:	Screening (Visit 1)	Pre-Dose	Cycle 1		1	C	Cycle 2		С	Cycle 3			cle	4	Weeks 18, 27, 36 & 45	Week 54 or early Termination	Survival Follow-up call
Days from injection (Safety assessment follow-up)	-28	0	1	8	15	1	8	15	1	8	15	1	8	15			
Scheduling Window (Days) unless specified otherwise	-28 to 0	-3 to 1 Pre- dose		+3			±3			±3			±3		±3	±3	Every 9 weeks (±7 days)
Informed Consent	X																
Inclusion/Exclusion Criteria	X	X 								Г							
Demographics and Medical History	X																
Disease history (including genetic information, dMMR/MSI and Tumour Mutational status)	Х																
Disease treatment history	X																
Prior and Concomitant Medication Review	X	X	X	X	X	X	X	X	X	X	X	X	X	X	Х	X	
Review Adverse Events	X	X	X	X	X	X	X	X	Х	X	X	X	X	X	X	X	
12-Lead Electrocardiogram (ECG) local reading	X		X 			X 			X 			X 				X	
12-Lead Electrocardiogram (ECG) central reading			X 									X3					
Full Physical Examination	X					Ī				Ī	1					X	

agalin A subsidiary of Bio		PRIVILEGED & CONFIDENTIAL
Investigational Product: AGI-134	A Phase I/IIa, multicentre, two-parts, open label study designed to evaluate the safety and tolerability of escalating doses of AGI-134 in unresectable/metastatic solid tumours.	Protocol No. AGI-134.FIM.101
Phase: I/IIa		Version 6.1 31 May 2021

Study Period:	Screening Phase	Baseline Assessments					3-	We	ek (	Сус	les				9-Week F.U Cycles	Termination Visit	Long-Term Follow-up
Treatment Cycle:	Screening (Visit 1)	Pre-Dose	Cycle 1			C	Cycle 2			Cycle 3			ycle	4	Weeks 18, 27, 36 & 45	Week 54 or early Termination	Survival Follow-up call
Days from injection (Safety assessment follow-up)	-28		1	8	15	1	8	15	1	8	15	1	8	15			
Scheduling Window (Days) unless specified otherwise	-28 to 0	-3 to 1 Pre- dose		+3			±3			±3			±3		±3	±3	Every 9 weeks (±7 days)

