Post-study Anti-Cancer Therapy Status																X 	Х
Survival Status																X 	X

- Inclusion/Exclusion Criteria should be re-assessed at Baseline prior to final eligibility confirmation
- A 12-lead ECG will be recorded at each cycle (1-4) prior to AGI-134 administration (up to 1 hour) and 2 hours after dose (±30 minutes). In cycle 1 and 4 when a Holter device is connected a printout should be extracted from the device at the appropriate timepoints

  In Cycle 1 and 4 a 12-lead ECG holter recording device will be connected to the subject 1-2 hours prior to AGI-134 administration and record ECG consecutively for at least 24 hours after AGI-134 administration
- Pre-dose only
- To be performed up to 1 hour prior to AGI-134 administrations and 1 hour post AGI-134 administration. On Cycle 1 and Cycle 4, to be performed also 72 hours post AGI-134 administration

- Vital signs will be collected up to 1 hour pre-dose and 0.5, 1, 24, 36, 48 and 72 hrs post AGI-134 administration
  Vital signs will be collected prior to AGI-134 administration and 2 hours post dose
  Refer to "Administration AGI-134 and Tumour Biopsy Procedures in Study AGI-134.FIM.101" for detailed information
- 10. All laboratory assessment should be performed before investigation product administration unless otherwise specified. Coagulation test results should be available before AGI-134 injections and biopsies
- Pregnancy test in Screening and Termination must be serum. At other visits should be a urine test
   HPV status assessment should be performed at local lab in case no available status from the time of HNSCC diagnosis
   To be drawn 72 hours post AGI-134 administration

- 14. To be drawn on Cycle 3, during week 8 (concomitant with biopsies)
  15. To be drawn up to 1 hour prior to AGI-134 administration and 0.5, 1, 2, 4, 6, 8, 12, 24, 36, 48 and 72 hrs post AGI-134 administration
- 16. To be drawn up to 1 hour prior to AGI-134 administration and 2 hours post dose
  17. The biopsies can be performed on the day of the first dose and up to 3 days prior
- 17. The biopsies can be performed on the day of the first dose and up to 3 days prior18. The biopsies should be performed on Cycle 3, during week 8

agalin A subsidiary of Bio		PRIVILEGED & CONFIDENTIAL

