Post-study Anti-Cancer Therapy Status											X	X
Disease and Survival Status											X	X

agalin A subsidiary of BIG		PRIVILEGED & CONFIDENTIAL
Investigational Product: AGI-134	A Phase I/IIa, multicentre, two-parts, open label study designed to evaluate the safety and tolerability of escalating doses of AGI-134 in unresectable/metastatic solid tumours.	Protocol No. AGI-134.FIM.101
Phase: I/IIa		Version 6.1 31 May 2021

- Inclusion/Exclusion Criteria should be re-assessed at Baseline prior to final eligibility confirmation.
- A 12-lead ECG will be recorded at each cycle (1-4) prior to AGI-134 administration (up to 1 hour) and 2 hours after dose (±30 minutes). In Cycle 1 and 3, when a Holter device is connected, a printout should be extracted from the device at the appropriate timepoints.
- In Cycle 1 and 3, a 12-lead ECG Holter recording device will be connected to the subject 1-2 hours prior to AGI-134 administration and record ECG consecutively for at least 24 hours after 3. AGI-134 administration.
- To be performed up to 1 hour prior and 1 hour post AGI-134 administration
- To be performed 48-72 hours post AGI-134 administration (prior to tumour biopsy if applicable) 6.
- Vital signs will be collected up to 1 hour pre-dose and 0.5, 1, 24, 36, 48 and 72 hrs post AGI-134 administration Vital signs will be collected prior to AGI-134 administration and 2 hours post dose
- AGI-134 should be administered on Day 1 of each Cycle. Refer to "Administration AGI-134 and Tumour Biopsy Procedures in Study AGI-134.FIM.101" for detailed
- All laboratory assessment should be performed before investigational product administration, unless otherwise specified. Pregnancy test in Screening and Termination Visit must be serum. At other visits a urine test. 10.
- 11.
- HPV status assessment should be performed at local lab in case no available status from the time of diagnosis.
- To be drawn pre-dose and 24 hours post AGI-134 administration
- 14. To be drawn pre-dose and at 2,6,12, and 24 hours post AGI-134 administration
- To be drawn pre-dose and at 2 and 6 hours post AGI-134 administrations 15.
- To be drawn up to 1 hour prior to AGI-134 administration and 0.5, 1, 2, 4, 6, 8, 12, 24, 36, 48 and 72 hrs post AGI-134 administration 16.
- To be drawn up to 1 hour prior to AGI-134 administration and 2 hours post dose
- 18. To be drawn 24 hours post AGI-134 administration

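### Section 5.4 allows Termination/ET safety bloods to be skipped on the strength of a result drawn before the last dose, in subjects who leave early after dose 2, 3 or 4

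*Combined protocol and SAP*

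**What the plan says.** Section 5.4 lists the Termination/ET procedures, which include CBC, biochemistry and thyroid tests, and then allows exceptions: "Exceptions for assessments may be provided in case these assessments were done 1-2 cycles prior to Termination visit". The Medical Monitor must agree to each one. No other condition is given. Safety bloods are not excluded from the exception, and nothing ties the earlier result to the date of the last dose. Imaging at the same visit, by contrast, has an explicit interval of at least 9 weeks since the last assessment.

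On the length of a cycle, Section 5.3 says: "AGI-134 administration is divided into cycles (each cycle is 3 weeks long". Table 6 in Appendix A also uses the word for the follow-up visits, under the column heading "9-Week F.U Cycles".

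On dosing and blood timing in Cycles 2 to 4, Section 5.3.4 says "AGI-134 will be administered on Day 1 of each cycle" and "each assessment should be performed before administration of the investigational product unless otherwise specified". The schedule footnotes agree: "All laboratory assessment should be performed before investigation product administration unless otherwise specified" (Table 6, Part 1) and "All laboratory assessment should be performed before investigational product administration, unless otherwise specified" (Table 7, Part 2).

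**The concern.** Whatever its nominal timing, the ET blood has one role that no other scheduled sample fills after dose 2, 3 or 4: it is the only planned CBC and biochemistry taken after the last dose. An exception that looks back one or two dosing cycles reaches to the other side of that dose. The subjects concerned include those who stopped because of an adverse event. Safety is the primary objective of this first-in-human study, and non-serious adverse events are recorded only to 30 days after the last dose (5.8.1, 7.1). For an early leaver, the ET blood is therefore the one scheduled chance to find a laboratory abnormality caused by that dose within the recording period.

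**Working it through.** No sample size or error rate is involved, so the check is a calendar.

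**Inputs**
- Doses on nominal study Days 1, 22, 43 and 64 (Day 1 of four 3-week cycles; 5.3, 5.3.4).
- Scheduled CBC and biochemistry: Baseline; Cycle 1 Days 3, 8 and 15 (5.3.2, 5.3.3; Table 6 gives 72 hours after dosing for the first of these); then once before dosing on Day 1 of Cycles 2, 3 and 4 (5.3.4, Tables 6 and 7). Table 6 has Day 8 and Day 15 columns for Cycles 2 to 4, but their CBC and biochemistry cells are blank.
- Weeks 18 to 45: no safety bloods. Long-term follow-up: telephone only (5.5).
- Age of the result under the exception: 1 × 21 = 21 to 2 × 21 = 42 days before the visit.

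**Formula.** Let d be the days from last dose to ET and a the age of the earlier result at ET. The result was drawn at t = d − a relative to the last dose, so the exception covers t from d − 42 to d − 21. After dose 2, 3 or 4 the latest scheduled draw before ET is at t = 0, before dosing, so a usable scheduled result cannot have t above 0.

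- d = 1 to 20: the range ends at t = −20 to −1, so everything in it precedes the day of the last dose.
- d = 21 to 42: the range includes t = 0, but the only draw on that day is before dosing. No scheduled draw falls at a positive t.
- d above 42: the range starts above 0 and holds no scheduled bloods, so the exception has no scheduled result to use.

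Checking each possible ET day with 3-week cycles gives:

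| Last dose | Scheduled CBC/biochemistry after last dose and before ET | ET days (after last dose) with a scheduled result 21–42 days old | ET days on which any such result follows the last dose |
|---|---|---|---|
| 1 | Days 3, 8, 15 | 20–56 | 34 |
| 2, 3 or 4 | none | 1–42 | 0 |

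**Example.** Last dose is dose 3 on Day 43 and ET is on Day 57, so d = 14. The range is Day 57 − 42 = 15 to Day 57 − 21 = 36. It contains Cycle 1 Day 15 and the Cycle 2 Day 1 pre-dose draw (Day 22). Both precede dose 2 as well as dose 3.

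The draws in the range are mostly Day 1 pre-dose bloods. For earlier last doses some Cycle 1 draws also fall in it; they follow dose 1 but still precede the last dose. The ±3-day visit windows change nothing, because blood and dose move together.

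**Other meaning of cycle.** With 9-week cycles the age is 63 to 126 days. ET visits with a scheduled result of that age run to 126 days after the last dose, and again none of those results follows the last dose.

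**Week 54.** Taking Week 54 as Day 378, the range is Week 48 to Week 51 (Week 36 to Week 45 with 9-week cycles). It lies after the last dose and holds no scheduled bloods. The last earlier draw is Day 64, which is (378 − 64) / 7 = 44.9 weeks before.

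**The case against.** The strongest reply is that each exception needs the Medical Monitor's approval, case by case, and that the Medical Monitor sits on the Safety Committee. Subjects who stop for an adverse event are followed to resolution or stabilisation (4.6, 5.4), abnormal laboratory results are repeated (5.8.6), and unscheduled laboratory tests are possible (5.6). A Day 1 visit at which the dose is withheld, such as Cycle 4 after a positive anti-Gal IgE, also yields bloods that follow the last dose. All of this stands, and it is why toxicity may be missed, not why it would be. It does not close the gap. The approval carries no timing criterion, and repeat testing presupposes an abnormality already found.

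A reader might infer more than the documents support:
- *That a pre-dose value becomes the Termination result and biases the laboratory summaries towards no change.* The text only permits an assessment to be excepted. It does not say whether the earlier value is carried forward or the visit is left missing. Section 8.2 defers detailed methods to an SAP that takes precedence, and the text available for this review does not settle the point. Section 8.2.2 also summarises toxicity by worst grade.
- *That all Termination samples are affected, including the immune ones.* In Part 2, flow cytometry is also drawn 24 hours after dose 3. In Part 1, anti-Gal, PBMC and FACS bloods are drawn in Week 8, after dose 3. A general claim does not hold.
- *That MTD and RP2D are compromised.* They rest on Cycle 1 DLTs, when post-dose bloods are scheduled.
- *That the reach is 9 to 18 weeks.* Section 5.3 sets administration cycles at 3 weeks. The longer reading arises only because Section 5.4 does not say which cycle it means.

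**Conclusion.** The point holds for Early Termination within about 6 weeks (1 to 42 days) of dose 2, 3 or 4. Followed as written, Section 5.4 can reduce such a subject's scheduled CBC and biochemistry after the last dose from one to none. This assumes 3-week cycles, every Day 1 dose given as scheduled, and no unscheduled bloods. It does not apply to Week 54 Termination, to subjects who received dose 1 only, or to the Cycle 1 DLT assessment.

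The number of subjects affected cannot be given. The plan foresees up to 24 subjects in Part 1 and about 35 in Part 2, but states no expected number of early leavers and no expected use of the exception. The loss of a post-dose observation is demonstrable from the schedule; bias in the safety analysis is possible only. The change should be made because the sample is the only one of its kind and the correction is small.

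**What to change.** Amend Section 5.4 so that an earlier laboratory safety result may replace a Termination/ET laboratory assessment only if it was obtained after the last AGI-134 dose, and state the allowed interval in days in place of cycles. Medical Monitor approval can stay as it is. The exception remains available where it is harmless, for example after unscheduled bloods or a Day 1 visit at which no dose was given. The cost is a one-sentence amendment and a few ET blood draws that might otherwise have been skipped.

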## **Termination / Early Termination Visit Procedures**

- · Review concomitant medications
- AEs Recording (AEs up to 30 days post last dose of study drug and SAEs up to 90 days post last dose of study drug)
- 12-lead electrocardiogram (ECG) local reading
- · Full physical examination
- Examination of injection site
- Vital signs (blood pressures, pulse rate, O2 saturation, oral temperature in °C, respiratory rate)
- Weight
- ECOG performance status
- Photography of all superficial injected lesions
- Blood will be drawn for:
  - o Pregnancy test in serum
  - o CBC with differential
  - o Biochemistry panel
  - o T3, free T4 and TSH
  - Flow cytometry
  - Anti-Gal antibodies IgG/IgM and sub classing
  - PBMC + cryopreservation
  - TCR Sequencing
  - RNA isolation (Gene expression/sequencing)
- In case Early Termination occurred prior to Cycle 3, every effort should be made to perform biopsies on the ET visit. Two biopsies should be taken:
  - From the tumour lesion to be injected
  - From the un-injected lesion

203		PRIVILEGED & CONFIDENTIAL
Investigational Product: AGI-134	A Phase I/IIa, multicentre, two-parts, open label study designed to evaluate the safety and tolerability of escalating	Protocol No. AGI-134.FIM.101
Phase: I/IIa	doses of AGI-134 in unresectable/metastatic solid tumours.	Version 6.1 31 May 2021

- Tumour Imaging Assessment will be required for termination visit at Week 54 or Early Termination visits, conducted ≥ 9 weeks from last imaging/ RECIST v 1.1 assessment.
- RECIST v 1.1 assessment will be done using imaging and/or superficial lesion measurement according to the tumour type. This assessment will be required for Termination visit at Week 54 or Early termination conducted ≥ 9 weeks from last imaging/ RECIST v 1.1 assessment. Post-Study Anti-Cancer Therapy Status (for early termination)
- Survival and disease status (for early termination)

## 5.5 Long-Term Follow-Up

All subjects, including early terminated subjects, will be contacted by phone every 9 weeks (±7 days) after Termination/ET visit (Week 54). This Follow-Up will continue for 5 years. During these phone calls, subjects will be asked to provide an update about disease status and post-study anti-cancer therapy received. During the first Long-Term follow-up visit, subjects should be questioned regarding the occurrence of AEs/SAEs and the outcome of any AEs/SAEs that were ongoing at the Termination/Early Termination visit. However, only AEs that occurred up to 30 days after the last dose of study drug and SAEs that occurred up to 90 days after the last dose of study drug will be recorded in the eCRF (see sections 7.1 and 7.2.2 for details). In case of death, every effort should be done in order to capture the date and reason for death. All the data will be collected and entered within the eCRF.

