### 3.1.1 Ongoing Safety Assessment and Dose-Limiting Toxicity

AEs will be reported from the time of informed consent signature up to 30 days after the last dose of study drug or until the initiation of new anti-cancer treatment, whichever is sooner. SAEs will be reported until 90 days after the last dose of study drug, or until the initiation of new anti-cancer treatment, whichever is sooner. The period considered for DLT assessment for Part 1 is defined as the time from the first dose administration of AGI-134 and up to the end of the first cycle of therapy (i.e. Cycle 1/Day 1 to Cycle 1/Day 21).

agalin A subsidiary of BIG	PRIVILEGED & CONFIDENTIAL
Investigational Product: AGI-134	Protocol No. AGI-134.FIM.101
Phase: I/IIa	Version 6.1 31 May 2021

The period considered for DLT assessment for Part 2 is defined as the time from the first dose administration of AGI-134 and up to the end of the first cycle of therapy (i.e. Cycle 1/Day 1 to Cycle 1/Day 21) for the first 3 subjects with deep lesions.

After the DLT assessment period, data will be assessed on an ongoing basis during the study. All AEs should be captured within the eCRF, however AEs reported beyond the DLT period will not be considered for the DLT assessment.

During Part 2 of the study, any specific AE that fits the DLT definition and occurs at a frequency of > 30% will stop accrual. In this scenario, the Safety Committee may recommend a lower dose level or dosing schedule change for the continuation of the expanded cohort. The study will be discontinued or terminated in case of an unacceptable risk or a negative change in the risk/benefit assessment. This might include the occurrence of adverse events for which character, severity or frequency is unexpected and overcome the potential benefit of the study drug. In addition, any data deriving from other clinical trials or toxicological studies which negatively influence the risk/benefit assessment might cause discontinuation or termination of the study.

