## 7.2.2 Reporting Period of Serious Adverse Event

Once the subject has signed the Informed Consent Form (ICF), SAEs will be recorded up to 90 days following the last dose of study drug or until the subject initiates new anti-cancer therapy, whichever is earlier. All SAEs will be followed up for outcome.

Any SAEs, or follow-up to a SAE should be reported within 24 hours to the Sponsor. This includes death due to any cause other than progression of the cancer under study, whether or not related to the investigational product.

Additionally, any SAE, considered by a qualified physician to be related to the Sponsor's product that is brought to the attention of the PI at any time after the Termination/ET visit and up to 5 years, must also be reported immediately to the Sponsor.

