- The biopsies can be performed on the day of the first dose and up to 7 days prior AGI-134 Injection Superficial only between  $48h\pm24$  hours post AGI-134 administration 19.
- 20.
- If done on the same day of AGI-134 administration, biopsy should be done prior to injection. If not on the same day, a window of -7 days prior AGI-134 administration is allowed
- In case of Early Termination occurring prior to Cycle 3, every effort must be made to perform biopsies on the ET visit Two biopsies should be taken.
- 23. CT or MRI (according to Imaging Manual) or superficial lesion measurement (depending on to the tumour type). In Cycle 3, to be done between Week 9 and Cycle 4 - Day 1 (before injection of AGI-134).
- AEs will be recorded up to 30 days after the last dose of study drug, and SAEs up to 90 or until the initiation of new anti-cancer therapy, whichever is sooner.
- For detailed time window for sample collection refer to the Laboratory Manual

agalin A subsidiary of BIO	PRIVILEGED & CONFIDENTIAL	
Investigational Product: AGI-134	A Phase I/IIa, multicentre, two-parts, open label study designed to evaluate the safety and tolerability of escalating	Protocol No. AGI-134.FIM.101
Phase: I/IIa		Version 6.1 31 May 2021

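### Section 5.5 and the two schedules give three different instructions for asking about SAEs after Early Termination; under Section 5.5, a subject who leaves mid-cycle can have the last 6 to 27 days of the 90-day SAE window unasked at nominal timing

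*Combined protocol and SAP*

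**What the plan says.** Section 7.2.2 fixes the period: "SAEs will be recorded up to 90 days following the last dose of study drug or until the subject initiates new anti-cancer therapy", whichever comes first. The window for non-serious AEs is shorter. Section 3.1.1 has them reported "up to 30 days after the last dose of study drug or until the initiation of new anti-cancer treatment, whichever is sooner".

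After the Termination or ET visit, contact is by telephone. Section 5.5 says that all subjects, early leavers included, "will be contacted by phone every 9 weeks (±7 days) after Termination/ET visit". The content of these recurring calls is given as follows: "During these phone calls, subjects will be asked to provide an update about disease status and post-study anti-cancer therapy received". Safety questions appear in one further sentence, tied to one call: "During the first Long-Term follow-up visit, subjects should be questioned regarding the occurrence of AEs/SAEs and the outcome of any AEs/SAEs". Section 5.5 then repeats that AEs to 30 days and SAEs to 90 days after the last dose are to be recorded.

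The two schedules in Appendix A differ from this text and from each other:

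- **Table 6 (Part 1)** marks the adverse-event review row from Screening through Termination and leaves the Long-Term Follow-up column blank.
- **Table 7 (Part 2)** marks the row in the Long-Term Follow-up column, which is headed as every 9 weeks, and attaches footnote 24: "AEs will be recorded up to 30 days after the last dose of study drug, and SAEs up to 90". The footnote prints no unit after 90, but days are clearly meant. It does not restrict the review to the first call.

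**The concern.** An enquiry can only cover the time before it is made. If the single safety enquiry named in Section 5.5 falls before Day 90, SAEs between that call and Day 90 are within the recording period, but nobody is instructed to ask about them.

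The people affected are those who stop early. Subjects still attending are asked about SAEs at the Week 27 visit, after their window has closed. Safety and tolerability is the primary objective of this first-in-human study, so it matters that the 90-day SAE count is collected in the same way for those who leave and those who stay. It also matters that sites in the two parts do not work from different instructions.

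**Working it through.** The protocol states no derived figure to reproduce; this is calendar arithmetic.

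**Inputs**

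- SAE window: 90 days after the last dose (Section 7.2.2).
- Calls: every 9 weeks = 63 days after the ET visit, ±7 days (Section 5.5).
- Cycle length: 21 days, extendable (Section 5.3).
- d = days from last dose to ET visit. The protocol does not fix this interval. I take d = 0 to 21 for a subject who leaves within a standard cycle.

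**Formulas**

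- First call (days after last dose) = d + 63, range d + 56 to d + 70.
- Unasked part of the window = max(0, 90 − first call).
- Second call = d + 126 ± 7.

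**Results under Section 5.5**

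| d | First call, nominal | Gap, nominal | Gap, call 7 days late | Gap, call 7 days early |
|---|---|---|---|---|
| 0 | Day 63 | 27 days | 20 | 34 |
| 7 | Day 70 | 20 days | 13 | 27 |
| 14 | Day 77 | 13 days | 6 | 20 |
| 21 | Day 84 | 6 days | 0 | 13 |

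The nominal gap is 27/90 = 30% of the window at d = 0 and 6/90 = 7% at d = 21.

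**Where the gap ends.** Setting 90 − (d + 63) = 0 gives d = 27. With a call 7 days late, 90 − (d + 70) = 0 gives d = 20; with a call 7 days early, 90 − (d + 56) = 0 gives d = 34.

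**A foreseeable case.** The first scheduled tumour assessment after baseline is in Week 9 (Section 5.12), that is Days 57 to 63. The Cycle 3 dose is nominally on Day 43. Exit on that assessment gives d = 14 to 20 and a nominal gap of 13 to 7 days.

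**Who is not affected**

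- Non-serious AEs: the earliest possible first call is Day 0 + 56 = Day 56, after the 30-day window has closed.
- Week 54 completers: the Cycle 4 dose is on Day 64 and Week 54 is Day 378, which is 378 − 64 = 314 days later. The Week 27 visit, 189 − 64 = 125 days after that dose, already looks back over the full 90 days.
- Exits around Week 18 after a Cycle 4 dose: d is about 126 − 64 = 62, well past the cut-off of 27.

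**The second call.** For d = 0 it falls on Day 126, and on Day 119 at the earliest. An SAE question there would cover the whole window for every d. Table 7 can be read as requiring this question in Part 2; Section 5.5 does not ask it, and Table 6 marks no review at any call.

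**The case against.** The strongest counter-argument is that Table 7 already provides for the review in Part 2, which is planned at about 35 subjects. A reader of Section 5.5 alone might infer that the study asks about SAEs only at the first call. The documents do not support that for Part 2, because the table marks AE review in the nine-weekly column. This stands, and it is why the point is one of reconciliation. It does not remove the problem: a Part 2 site that follows the text asks once, and Part 1 has no support from its own schedule.

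A reader might also infer that everyone who leaves mid-cycle has a gap. That is too broad. Cycles may be extended, Section 6.7.4 allows interruptions of up to 3 weeks, and at d of 27 or more the nominal gap is zero. It is also zero at d = 20 or 21 if the call is made 7 days late. Starting new anti-cancer therapy closes the window early. The 27-day figure needs an ET visit on the dosing day and should be read as the nominal upper end.

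Other routes narrow the loss:

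- AEs that lead to withdrawal are followed until resolved or stable (Sections 4.6 and 5.4).
- Date and reason for death are sought during long-term follow-up (Section 5.5).
- Subjects are told to contact the site about changes in well-being (Section 5.2).
- Related SAEs that come to the investigator's attention remain reportable for up to 5 years (Section 7.2.2).

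These points are fair, but none solicits a new non-fatal SAE. The 5-year route covers related events only, whereas the 90-day rule covers all SAEs.

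Two further inferences should be resisted. The documents give no drop-out or SAE rate, so the number of missed SAEs cannot be estimated from them. They also do not show that late SAEs are more likely in early leavers.

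**Conclusion.** The point holds as an inconsistency with a dated consequence. Section 5.5, Table 6 and Table 7 cannot all be followed. Under Section 5.5, a subject whose ET visit is 0 to 21 days after the last dose has 27 to 6 days of the SAE window without a scheduled enquiry at nominal timing (20 to 0 with a late call, 34 to 13 with an early one).

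This rests on the assumed range for d and on no new anti-cancer therapy having started before Day 90. The defect is in active solicitation; SAEs that are volunteered are still recorded. It concerns SAEs only. A reader might infer that dose finding is compromised, but the DLT period is Cycle 1 Day 1 to Day 21, so determination of the MTD and RP2D is not touched.

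**What to change.** Reconcile the three places.

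1. In Section 5.5, keep the AE/SAE questions at the first call for all subjects and add: *If the first call is made less than 90 days after the last dose, SAEs will also be asked about at the next scheduled call, covering the period up to 90 days after the last dose or the start of new anti-cancer therapy, whichever is sooner.*
2. Mark the same review in the Long-Term Follow-up column of Table 6.
3. Word footnote 24 of Table 7 to match, with the unit stated.

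The first-call questions should not be made conditional on new therapy. A subject who starts therapy before that call still needs to be asked about SAEs between the ET visit and the start of therapy, and about the outcome of ongoing events. New therapy should limit the period asked about and leave the asking in place.

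The cost is protocol wording and one extra question at a call already scheduled. No visit, contact or subject is added.
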